### **9.3.3 PAH Therapy**

The listing of PAH Concomitant Medications will include subject, previous study, and all concomitant PAH medications that were denoted as either ongoing at the start of the TDE-PH-304 study or added during the TDE-PH-304 study (start date of medication is on or after start date of study enrollment), with appropriate designation. The correspondence of raw concomitant medication names to coded generic terms will be listed. The summaries of PAH concomitant medications will be separated by those ongoing at the start of the TDE-PH-304 study and those added during the TDE-PH-304 study. These summaries will be provided by previous study and overall, and will include the number (percent) of subjects reporting each WHO Drug Dictionary medication name, as well as the number of records for each medication name. The PAH medications that were added during the TDE-PH-304 study will also be categorically summarized by PAH therapy class (ERA, PDE-5i, oral/inhaled prostacyclin, parenteral prostacyclin, and none) within each previous study and overall.

### **9.3.4 Concomitant Therapy**

The listing of Other Concomitant Medications will include subject, previous study, and all concomitant medications that were reported during the study (start date of medication is on or after start date of study enrollment). The summary will be provided by previous study and overall and will include the number (percent) of subjects reporting each medication category (as specified on the CRF), as well as the number of records for each medication category, at each scheduled visit.

## **10 EFFICACY ANALYSES**

### **10.1 SIX MINUTE WALK TEST**

The listing of six minute walk distance (6MWD) will include subject, previous study, and all reported 6MWDs, and their associated Borg Dyspnea Scores. The summaries of 6MWD at Month 12 will be provided by previous study and overall, treatment assignment in previous study (active/placebo), PAH medication use (no new therapy added/new PAH therapy added), PAH etiology (idiopathic/familial, collagen vascular disease, other), baseline WHO functional class, and dosing quartiles and tertiles. The summaries will include a categorical summary of current status, as well as descriptive statistics for baseline 6MWD, 6MWD at Month 12, and the change in 6MWD from baseline to Month 12.

Achievement of a walk distance of at least 380 meters at Month 12 will be summarized by previous study and overall. Achievers and non-achievers will then be summarized based on their baseline walk ( $\leq 380$  meters vs.  $> 380$  meters) by previous study and overall.

Note that all six-minute walk test summaries will exclude subjects from study TDE-PH-205 since the goal of that study was to maintain six-minute walk test performance after transition; thus, no improvements were expected. All associated listings, however, will include the subjects from TDE-PH-205.

The summaries of the Borg Dyspnea Score at Month 12 will be provided by previous study and overall, previous study treatment assignment, and PAH medication use. The summaries will include a categorical summary of current status, as well as descriptive statistics for baseline Borg Dyspnea Score, Borg Dyspnea Score at Month 12, and the change in Borg Dyspnea Score from baseline to Month 12. Note that the Borg Dyspnea Score summaries will exclude subjects from study TDE-PH-205 since the goal of that study was to maintain six-minute walk test performance after transition; thus, no improvements were expected.

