Study Visit Schedule: Study visits will be timed to occur 3, 6, 12, 24, 36 months after each subject's first exposure to UT-15C SR. The study will continue with yearly visits beyond 36 months until either UT-15C SR is approved by the appropriate regulatory authorities or the study is discontinued by the sponsor. Subjects receiving placebo in the previous study (TDE-PH-301, TDE-PH-302, or TDE-PH-308) and subjects enrolled from the TDE-PH-202 study who were in Dose Groups 1 or 2 and permanently discontinued treatment must be contacted weekly by telephone during the first 12 weeks of the open-label study. Subjects transitioning from BID to TID dosing should be contacted weekly for the first four weeks after transitioning. Monthly telephone calls must be conducted for all subjects actively participating in TDE-PH-304, regardless of study drug allocation (UT-15C SR or placebo) in the previous study. In addition to the scheduled study visits, all subjects must be seen in the clinic no less than once every six months for routine standard of care medical evaluation.

Efficacy Assessment: A 6-Minute Walk Test with Borg Dyspnea Score will be conducted at the study visit occurring 1 year after the subject first received UT-15C SR.

Safety Assessments: Adverse events and clinical laboratory parameters will be assessed throughout the study.

Statistical Considerations: All data will be summarized in tables and listings.

Sponsor: United Therapeutics Corporation
[name]
[name]
[name]
United States of America

TABLE OF CONTENTS

LIST OF CONTACTS FOR STUDY	2
INVESTIGATOR AGREEMENT	3
PROTOCOL SUMMARY.....	4
TABLE OF CONTENTS	6
LIST OF ABBREVIATIONS	8
1 BACKGROUND AND RATIONALE.....	9
1.1 Pulmonary Arterial Hypertension: Definition of Clinical Problem	9
1.2 Treprostinil Background	9
1.2.1 UT-15C SR Nonclinical	9
1.2.2 UT-15C SR Clinical Pharmacology	11
1.2.3 Remodulin Experience	13
1.3 Rationale for Development of Study Drug in Disease/Condition.....	13
1.4 Clinical Hypothesis.....	14
2 STUDY OBJECTIVES AND ENDPOINTS	14
2.1 Study Objectives.....	14
2.2 Study Endpoints	14
3 EXPERIMENTAL PLAN	14
3.1 Study Design.....	14
3.2 Overall Schedule of Times and Events	15
3.3 Clinical Assessments.....	16
3.3.1 Efficacy.....	16
3.3.2 Safety	16
3.4 Number of Centers.....	17
3.5 Number of Subjects	17
3.6 Estimated Study Duration	17
4 SUBJECT ELIGIBILITY.....	18
4.1 Subject Inclusion Criteria	18
5 SUBJECT ENROLLMENT	19

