⁴ **Visit windows** are ± 1 month from the scheduled number of months from first exposure to UT-15C SR, except for Visit 1, which is ± 2 weeks.

⁵ **VISIT 1** – Only for subjects randomized to placebo in TDE-PH-301, 302, or 308; 3 months after subject's first exposure to UT-15C. Also applies to subjects enrolled from the TDE-PH-202 study who are beginning a dose of 0.25mg BID.

VISIT 2 – 6 months after subject's first exposure to UT-15C SR.

VISIT 3 – 12 months after subject's first exposure to UT-15C SR.

VISIT 4 – 24 months after subject's first exposure to UT-15C SR.

VISIT 5 – 36 months after subject's first exposure to UT-15C SR.

⁶ **Weekly telephone call** required for 4 weeks for all subjects who transition from a BID to TID regimen to assess dose titration needs, potential adverse events, concomitant medication usage and PAH signs and symptoms.

⁷ **Monthly telephone calls** (at a minimum) required for all subjects participating in TDE-PH-304 to assess dose titration needs, potential adverse events, concomitant medication usage and PAH signs and symptoms.

⁸ **Visits beyond Visit 5** will occur yearly until either the drug receives regulatory approval in a particular region or the sponsor discontinues the study. Assessments after visit 5 will include adverse events, PAH concomitant medications, concomitant medications, clinical laboratories, and compliance/drug accountability.

⁹ **EXIT** – If the subject discontinues from the study between scheduled visits, every effort should be made to obtain the exit assessments just prior to termination from the study.

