3.3.2.3. Concomitant Medications

In this open-label study, there are no restrictions on concomitant medications, with the exception of the addition of prostanoid therapy. If chronic parenteral prostanoid therapy is added for the treatment of worsening PAH, the subject will be discontinued from the study. Short term, parenteral prostanoid therapy may be initiated if required (e.g., the patient is temporarily unable to take oral medications). If prostanoid therapy is initiated for any other reason than worsening PAH, eligibility for continued participation in this study will need to be reviewed by the Medical Monitor on a case by case basis. For subjects enrolling into TDE-PH-304 from the TDE-PH-203 study continued chronic use of inhaled treprostinil (Tyvaso®) is acceptable.

ERAs and PDE-5 inhibitors may be added or withdrawn at any time. Concomitant PDE-5 inhibitors, ERAs, and other medications related to the subject's treatment will be collected at each study visit and recorded in the CRF.

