- Drug accountability/compliance
- 6-Minute walk test/borg dyspnea score

Visit 4 (24 months after first dose of UT-15C SR)

- Adverse events
- PAH concomitant medications
- Concomitant medications
- Clinical laboratories
- Drug accountability/compliance

Visit 5 (36 months after first dose of UT-15C SR)

- Adverse events
- PAH concomitant medications
- Concomitant medications
- Clinical laboratories
- Drug accountability/compliance

Yearly visits beyond 36 months

- Adverse events
- PAH concomitant medications
- Concomitant medications
- Clinical laboratories
- Drug accountability/compliance

Exit (premature discontinuation)

- Adverse events
- PAH concomitant medications

- Concomitant medications
- Clinical laboratories
- Drug accountability/compliance

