8 STUDY TERMINATION

8.1 Subject Discontinuation

A subject may voluntarily withdraw or be withdrawn from the study by the Investigator at any time for reasons including, but not limited to, the following:

- The subject wishes to withdraw from further participation.
- A serious or life-threatening AE occurs or the Investigator considers that it is necessary to discontinue study drug to protect the safety of the subject.
- The subject deviated from the protocol.
- The subject's behavior is likely to undermine the validity of his/her results.
- The subject becomes pregnant

If a subject is discontinued prematurely, the Investigator must provide an explanation in the CRF (Investigator's Comment Log) and complete the End of Study Record for that subject. If study drug has been administered, the Investigator should make every effort to perform all scheduled evaluations prior to discharge. In the event that a subject discontinues prematurely due to an AE, the subject will be followed until the Investigator determines the AE has resolved, the AE is no longer considered clinically significant, the subject is lost to follow-up, or for 30 days following discontinuation of UT-15C.

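### The Month 12 walk and Borg change and the 380 m rate are in effect observed-case summaries, and no rule brings in subjects who die, progress or leave before Visit 3

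*SAP*

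**What the plan says.** The Protocol Summary states that "A 6-Minute Walk Test with Borg Dyspnea Score will be conducted at the study visit occurring 1 year after" first receipt of UT-15C SR. Protocol Table 3.2 marks the walk and Borg score at Visit 3 only, and neither its EXIT column nor the exit list in Protocol 7.1 contains a walk.

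Two passages ask for effort at early exit. Footnote 9 of Table 3.2 says "every effort should be made to obtain the exit assessments just prior to termination from the study", and Protocol 8.1 says "the Investigator should make every effort to perform all scheduled evaluations prior to discharge". Neither makes the walk an exit assessment.

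Some losses follow from worsening by rule. Protocol 3.3.2.3 says: "If chronic parenteral prostanoid therapy is added for the treatment of worsening PAH, the subject will be discontinued from the study".

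For the walk tables, SAP 10.1 says "The summaries will include a categorical summary of current status", followed by "as well as descriptive statistics for baseline 6MWD, 6MWD at Month 12, and the change in 6MWD from baseline to Month 12". The Borg tables have the same structure. SAP 10.1 also says "Achievement of a walk distance of at least 380 meters at Month 12 will be summarized by previous study and overall", and then splits achievers and non-achievers by baseline walk. TDE-PH-205 subjects are left out of all walk and Borg summaries.

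SAP 8.2 has missing data in its heading but lists only reasons for withdrawal. SAP 8 summarises available data. SAP 10.2 plans counts and Kaplan-Meier curves for death, discontinuation, and composites with progression or added PAH therapy.

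**The concern.** The change from baseline exists only for subjects who walked at Month 12. A subject who died, was removed for worsening PAH or left for another reason before Visit 3 contributes nothing to it. Some of these losses are tied to the outcome, and the study has no control arm to offset the selection. If leavers would have walked less far, the observed change looks better than the experience of the subjects who started treatment.

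Two smaller gaps need no assumption about leavers.

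- **380 m table.** It has no stated denominator and no rule for a subject without a Month 12 walk, so two programmers could report different rates from the same data. SAP 5 plans interim soft locks as often as yearly, at which subjects not yet due at Month 12 could be mixed with subjects who left.
- **Baseline.** Baseline 6MWD is not restricted to walkers, so the baseline and Month 12 means in one table may describe different subjects. The change itself is necessarily paired.

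At stake are the figures that answer the exercise objective.

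**Working it through.** **Plan's own figure.** There is none to reproduce. The sample size of about 900 is an enrolment expectation (SAP 6). The documents give no dropout rate, expected change, SD or achievement rate for the walk, so every input below is an assumption chosen to show a range.

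**Assumed inputs.** Walkers' change is normal with mean +20 m and SD 70 m. The share without a Month 12 walk is m = 15%, 25% or 35%. Among walkers, 55% reach 380 m.

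**Step 1: all missing subjects ranked below every walker.** The overall median is the walkers' quantile at (0.5 - m)/(1 - m), so median = 20 + 70 × z[(0.5 - m)/(1 - m)].

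| m | quantile | z | median |
|---|---|---|---|
| 15% | 0.412 | -0.223 | +4.4 m |
| 25% | 0.333 | -0.431 | -10.2 m |
| 35% | 0.231 | -0.736 | -31.5 m |

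The walkers' median is +20 m throughout. This is the severe end, because it treats every withdrawal as a worst outcome.

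**Step 2: only deaths and progression exits ranked worst.** Assume these are half of the losses and leave the other exits out. The share ranked worst is then d = (m/2)/(1 - m/2), which replaces m in the formula.

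| m | d | quantile | z | median |
|---|---|---|---|---|
| 15% | 8.1% | 0.456 | -0.111 | +12.2 m |
| 25% | 14.3% | 0.417 | -0.210 | +5.3 m |
| 35% | 21.2% | 0.365 | -0.344 | -4.1 m |

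If 25% or more of the analysed subjects are ranked worst, the lower quartile falls in that group and has no value in metres. Step 1 reaches this at m = 25%. Step 2 reaches it only at m = 40%, where d = 0.20/0.80 = 25%.

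**Step 3: mean change.** The walkers' mean minus the all-subject mean equals the share missing times the gap between walkers and leavers. With 10% to 40% missing and a gap of 0 to 100 m, this runs from 0 to 0.40 × 100 = 40 m. It is zero if leavers would have done no worse.

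**Step 4: the 380 m rate.** Achievers as a share of all eligible subjects = 0.55 × (1 - m).

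| m | among walkers | among all eligible |
|---|---|---|
| 15% | 55% | 46.8% |
| 25% | 55% | 41.3% |
| 35% | 55% | 35.8% |

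Both columns are compatible with SAP 10.1 as written, because the denominator is not stated.

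**The case against.** The strongest reply is that the plan already reports the loss. The sentence that plans the change also plans a status summary in the same table. In SAP 11.1 that status distinguishes death, progression of PAH, adverse event, withdrawn consent and loss to follow-up. SAP 10.2 adds event counts and survival curves. The study is unpowered and non-randomised, SAP 10.1 plans no test, and observed-case reporting is common for such a study. All of this stands, and it rules out any suggestion that the loss is hidden. It does not supply a denominator for the 380 m table, and none of these displays changes the two figures that address the exercise objective.

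A reader might infer that the exercise objective promises a result for everyone enrolled. The documents do not support that. The wording that ties an objective to the enrolled subjects belongs to the safety objective. The exercise objective speaks of continued therapy after one year, and the endpoint is measured once a subject has completed that year. The point therefore concerns interpretation and an undefined rule; the analysis does not contradict the stated objective.

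A reader might also take SAP 10.1 to exclude deaths from the 380 m table. It neither includes nor excludes them.

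Finally, counting every exit as a failure is itself a debatable choice, since someone who withdrew consent might have walked 380 m. That objection is right and shapes the fix.

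**Conclusion.** The concern holds in a limited form. The Month 12 6MWD and Borg changes are in effect observed-case summaries. The 380 m rate has no defined denominator. No rule brings subjects lost before Visit 3 into either. Overstatement of maintained capacity is the likely direction if leavers would have done worse, and removal for worsening PAH makes that plausible.

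It would go too far to say that capacity is overstated as a fact, because the documents contain no walk data on leavers and no dropout rate. Nor are leavers wholly unwalked: they lack a Month 12 and an exit walk, but SAP 10.1 summarises a baseline walk and lists all reported distances.

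Under the assumed inputs, a walkers' median of +20 m falls to about +12, +5 or -4 m when deaths and progression exits are half of a 15%, 25% or 35% loss and other exits are left out. It falls to +4, -10 or -32 m when every missing subject is ranked worst. The first set matches the analysis proposed below.

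**What to change.** Amend SAP 10.1, keeping the TDE-PH-205 exclusion.

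1. **Tables 14.2.1.10 and 14.2.1.11.** Report achievement among those who walked. Beside it, report achievement among all treated subjects whose Month 12 window has closed by the data cutoff. In the second version, count deaths and PAH-progression exits as non-achievers, and show other exits as a separate no-walk category within the denominator.
2. **6MWD and Borg tables.** State the number walked over the number eligible. Give baseline, Month 12 and change for the same walked subjects, and baseline for those without a walk, by status.
3. **Supplementary median change.** Beside the observed figures, show the median with deaths and PAH-progression exits ranked worst. State that other exits are left out, and that a quartile falling in the ranked-worst group is reported as such and not in metres.
4. **Conclusion.** Limit what is said from the observed change to subjects who walked at Month 12.

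The cost is SAP wording and a few extra table rows, using data already collected. The downside for the sponsor is a less favourable achievement rate and median beside the observed ones. No exit walk is needed.

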## 10.2 CLINICAL EVENTS

Clinical events, including death, study discontinuation for any reason, addition of PAH therapy, and addition of parenteral PAH therapy, will be listed, including date of each event, if applicable, as well as the subject's previous background therapy status (naïve, single background therapy, or double background therapy). Note that events may have occurred during the parent study for those subjects treated with active drug during the parent study, thus event data from the parent study will be included in these data analyses. The following combinations of clinical events will be utilized for summarization and plotting purposes, separately:

- Study discontinuation for any reason
- Death or discontinuation due to disease progression
- Death, discontinuation due to disease progression or addition of PAH therapy
- Death, discontinuation due to disease progression or addition of parenteral PAH therapy
- Death

Summary tables will be produced by previous study and overall and will display the number (percent) of subjects who experienced each event combination detailed above. Kaplan-Meier (K-M) curves for the above combinations of clinical events will be provided separately. Each K-M plot will include a time to clinical event curve for each of the previous studies overlaid on the same plot.

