4 SUBJECT ELIGIBILITY

4.1 Subject Inclusion Criteria

A subject is eligible for inclusion in this study if all of the following criteria apply:

1. The subject has remained on study drug and completed all assessments during the Treatment Phase of the previous study (TDE-PH-202, TDE-PH-203, TDE-PH-205, TDE-PH-301, TDE-PH-302, or TDE-PH-308 (or other studies evaluating PAH))
OR
The subject permanently discontinued study drug during the Treatment Phase of the previous study (TDE-PH-301, TDE-PH-302, or TDE-PH-308) due to clinical worsening, completed premature termination assessments prior to discontinuing study drug, completed all remaining scheduled study visits AND received placebo during the Treatment Phase of the previous study (TDE-PH-301, TDE-PH-302, or TDE-PH-308).
OR
The subject was randomized into Dose Group 1 or Dose Group 2 in the TDE-PH-202, permanently discontinued study drug during the 12-week Treatment Phase due to clinical worsening, completed all premature termination assessments prior to discontinuing study drug and completed all remaining scheduled study visits and assessments (with the exception of the hemodynamic measurements) through Week 12. Such subjects should start treatment with UT-15C in the open-label study at 0.25 mg BID.
2. The subject voluntarily gives informed consent to participate in the study.
3. Women of child bearing potential include any female who has experienced menarche and who has not undergone successful surgical sterilization (hysterectomy, bilateral tubal ligation or bilateral oophorectomy) or is not postmenopausal [defined as amenorrhea for at least 12 consecutive months]. Sexually active women of childbearing potential must use two effective forms of contraception during the length of the study. Medically acceptable forms of effective contraception include: (1) approved hormonal contraceptives (such as birth control pills), (2) barrier methods (such as a condom or diaphragm) used with a spermicide, (3) an intrauterine device (IUD), (4) partner vasectomy, or (5) abstinence. Males participating in the study must use a condom during the length of the study, and for at least 48 hours after discontinuing study medication.

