4.2 Subject Exclusion Criteria

1. The subject permanently discontinued study drug during the previous study (TDE-PH-202, TDE-PH-203, TDE-PH-205, TDE-PH-301, TDE-PH-302, or TDE-PH-308) due to treatment related adverse events.
2. The subject permanently discontinued study drug during the Treatment Phase of the previous study (TDE-PH-202, TDE-PH-203, TDE-PH-205, TDE-PH-301, TDE-PH-302, or TDE-PH-308) due to clinical worsening (as defined in those study protocols) and did not undergo premature termination assessments prior to discontinuing study drug, and/or did not complete all remaining study visits through the final scheduled visit.
3. The subject permanently discontinued study drug during the Treatment Phase of the previous study (TDE-PH-301, TDE-PH-302, or TDE-PH-308) due to clinical worsening, completed premature termination assessments prior to discontinuing study drug, completed all remaining scheduled study visits AND received UT-15C SR during the Treatment Phase of the previous study (TDE-PH-301, TDE-PH-302, or TDE-PH-308).

Subjects enrolled in the TDE-PH-202 study who were randomized into the iMTD group who clinically worsen may not participate. Subjects who permanently discontinue study drug during

the 12-week Treatment Phase due to treatment related adverse events are not eligible even if they complete all remaining scheduled study visits. Subjects who permanently discontinue study drug during the 12-week Treatment Phase and do not undergo premature termination assessments prior to discontinuing study drug and/or who do not complete all remaining study visits through the Week 12 visit are also not eligible.

4. The subject must not have developed any concurrent illness or condition during the conduct of the previous study, including but not restricted to, sleep apnea, chronic renal insufficiency, anemia, uncontrolled systemic hypertension or left sided heart disease, unless their physician feels that entry into this study would not be detrimental to their overall health.

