#### **7 ANALYSIS POPULATIONS**

All available data from all subjects enrolled in the TDE-PH-304 study will be used as detailed in this analysis plan. Additionally, subjects who were treated with active drug during the parent study and who enrolled in the TDE-PH-304 study will have the data from the parent study included in the data analyses and listings for this study, as detailed in this SAP.

Subjects who were treated with placebo during the parent study and who enrolled in the TDE-PH-304 study will have baseline data only from the parent study included in the data analyses and listings for this study, as detailed in this SAP.

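### SAP 10.2 brings parent-study events into the Kaplan-Meier curves without a time origin or entry rule; counted from first active dose, parent time is event-free by selection for death and almost so for study discontinuation

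*SAP*

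**What the plan says.** SAP 10.2 (Clinical Events) defines five event combinations, built from death, study discontinuation, discontinuation for disease progression, added PAH therapy and added parenteral PAH therapy. Its only statement on timing is: "Note that events may have occurred during the parent study for those subjects treated with active drug during the parent study", followed by "thus event data from the parent study will be included in these data analyses". On display it says: "Each K-M plot will include a time to clinical event curve for each of the previous studies overlaid on the same plot". It states no time zero, risk-set entry rule or censoring rule.

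SAP 7 (Analysis Populations) limits the analysis to subjects enrolled in TDE-PH-304. Active-parent subjects "will have the data from the parent study included in the data analyses and listings for this study". Placebo-parent subjects "will have baseline data only from the parent study included in the data analyses and listings for this study".

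Protocol 4.1 and 4.2 set the entry conditions. The main route is: "The subject has remained on study drug and completed all assessments during the Treatment Phase of the previous study". A second route admits placebo subjects who worsened but completed their visits. A third admits TDE-PH-202 Dose Group 1 or 2 subjects who "permanently discontinued study drug during the 12-week Treatment Phase due to clinical worsening", if they completed the remaining visits. Exclusion 3 bars TDE-PH-301, 302 and 308 subjects who stopped drug for worsening, "completed all remaining scheduled study visits AND received UT-15C SR during the Treatment Phase of the previous study". Exclusion 1 bars anyone who stopped for treatment-related adverse events.

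SAP 8 adds two subjects who were withdrawn from TDE-PH-301 at a drug recall and then enrolled directly. Their TDE-PH-301 arm is not stated. They are pooled with the 200-series studies.

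**The concern.** A subject appears in these curves only after getting through the parent study. If an active-parent subject's clock starts at the first parent-study dose, the period up to TDE-PH-304 entry counts as time at risk although a death in it is impossible. This is immortal time, and it pushes the curve up.

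The push differs between curves. The 200-series parents were open-label, so nearly every subject in that pooled row carries the window. The TDE-PH-301/308 and TDE-PH-302 rows mix active-parent subjects, who carry it, with placebo-parent subjects, who do not. Rows with equal hazards would plot apart, yet SAP 8.1 gives examining the impact of the previous study as the reason for summarising by it. SAP 5 says the outputs support regulatory submissions and long-term safety monitoring. With no test attached, the plotted curve is itself the result.

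**Working it through.** The plan states no Kaplan-Meier estimate, so there is no figure of its own to reproduce.

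**Step 1: the origin.** Parent-study events can have non-negative times on a curve only if the clock is already running in the parent study. SAP 3 times visits from first UT-15C SR, and SAP 11.1 counts parent exposure for active-parent subjects. Both point to first active dose. This is an inference.

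**Step 2: what can happen in the parent window of an enrolled active-parent subject.**

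| Component | Possible? | Why |
|---|---|---|
| Death | No | The subject later enrolled |
| Study discontinuation | No, except possibly the two recall subjects | Every route in inclusion 1 needs completed assessments or visits |
| Discontinuation for progression | Undefined for TDE-PH-202 Dose Group 1/2 re-starters; otherwise no | They stopped drug but completed the study |
| Added PAH therapy | Yes | Not barred by the entry criteria |

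**Step 3: size.** Inputs: window g = 12 weeks (TDE-PH-202 Treatment Phase, Protocol 4.1) and a 52-week year. Assumptions: constant hazard; true one-year event-free rate S of 95%, 90% or 80%; active-parent share a of 1 or 0.5.

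Plotted rate = a × S^((52 − g)/52) + (1 − a) × S

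For g = 12 the exponent is 40/52 = 0.769.

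| True S | All active | Half active |
|---|---|---|
| 95% | 96.1% (+1.1) | 95.6% (+0.6) |
| 90% | 92.2% (+2.2) | 91.1% (+1.1) |
| 80% | 84.2% (+4.2) | 82.1% (+2.1) |

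Two rows with the same hazard would thus differ by 0.6 to 2.1 points at one year. At three years the all-active rate is S^(3 − 12/52) against S^3, a shift of +1.0, +1.8 and +2.7 points.

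The documents give no other parent duration. If g were 24 weeks (assumed), the all-active rates would be 97.3%, 94.5% and 88.7%, and the half-active rates 96.1%, 92.2% and 84.3%.

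**Step 4: does delayed entry repair it?** In a simulation of 900 enrolled subjects, half active-parent, with g = 12 and 60 replicates, a true 90% gave 91.0% from the standard estimator and 89.9% with delayed entry. A true 80% gave 82.0% and 80.0%.

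There is a limit. If all subjects in a row are active-parent and enter at week 12, the risk set before week 12 is empty and every later risk set is unchanged. Delayed entry then returns the same S^(40/52), which is 84.2% for S = 80%. That is the correct value of survival to one year given event-free at week 12, not of survival from first dose. A half-active row under delayed entry, restarted at 1 at week 12, gives S/S^(12/52) = S^(40/52), the same 84.2%. The rows therefore agree only when read from a common starting week.

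**The case against.** The strongest reply is that the bias depends on how a gap is filled. The sentence on parent-study events precedes the listing, the count tables and the curves alike, and it does not mention time zero. Parent events could feed the tables only. That stands: a reader might infer that the SAP prescribes first active dose as the origin, and it does not. First active dose is nevertheless the origin that agrees with the SAP's other clocks, and the alternative is to leave five figures to the programmer.

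A reader might also infer that no active-parent subject could have discontinued, so that the death, any-discontinuation and death-or-progression figures are all flat over the parent period. The documents support this for death only. The two recall subjects could be parent-study discontinuations if they were on active drug. The SAP does not say whether a TDE-PH-202 drug stop for worsening counts as discontinuation due to progression. The two composites with added PAH therapy can contain genuine parent-study events, so including parent data has a legitimate purpose.

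It is also fair to say that the curves are descriptive, that the sample size was not powered (SAP 6), and that the previous-study populations differ by design, so the overlay was never a clean comparison. This limits the consequence. It does not excuse a further difference created by the clock.

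**Conclusion.** The point holds in a limited form. Following SAP 10.2 in the way that best fits the rest of the plan gives curves that overstate event-free survival for death and, almost entirely, for study discontinuation, by amounts that depend on each row's active share. The illustrated size is about 1 to 4 points at one year in an all-active row and about half that in a half-active row. This rests on a constant hazard, assumed event rates and active shares, and the 12-week window, which is documented for TDE-PH-202 alone. A reader might infer shifts near 9 points from a 24-week window, but no document gives that duration. Nor should this be read as undermining a hypothesis test, because none is planned on these curves. It should be corrected before the next soft lock because the error runs in the favourable direction and is cheap to remove.

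**What to change.** In SAP 10.2:

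- State that time zero is the first active UT-15C SR dose and that active-parent subjects enter the risk set only at TDE-PH-304 enrolment (delayed entry). Include the re-starters and the recall subjects by name of group, and state the censoring rule.
- Print numbers at risk. Where a row has few or no subjects at risk early on, as the 200-series row will, start the curve at a stated week and label it as conditional on being event-free then. Use the same week for all curves in an overlay.
- Define discontinuation due to disease progression as study discontinuation for that reason.
- For the two composites with added PAH therapy, count additions from TDE-PH-304 entry in the curve and report parent-study additions in the summary table.

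A curve from TDE-PH-304 start may be shown as an alternative, labelled as such. It should not be the only display, because it aligns subjects new to the drug with subjects already exposed and departs from the plan's time-on-drug convention. A sensitivity display that counts the re-starters' TDE-PH-202 worsening is optional.

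The cost is a few SAP sentences, some extra programming and smaller early risk sets. First active dose dates are already listed (SAP 9.1) and the enrolment date is already used to classify medications (SAP 9.3.3). No protocol amendment, visit or new data is needed.
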